### **Purpose:**

To evaluate the accuracy and precision of a novel adenosine-independent index of coronary artery stenosis, the resting flow reserve, against the instantaneous wave-free ratio and fractional flow reserve.

### **Background:**

Fractional flow reserve (FFR) measurement under hyperemic conditions is the invasive gold standard for determining the physiologic extent of cardiac ischemia (1). FFR has been validated in several clinical outcomes studies as a way of optimizing case selection for PCI. (1, 2) Recently two large-scale randomized controlled trials using a non-hyperemic resting measurement, the instantaneous wave free ratio (iFR), showed non-inferiority in major adverse cardiovascular events (MACE) comparing iFR to FFR for physiological assessment of moderate coronary stenosis (3,4). Moreover, these studies demonstrated a dramatic reduction in patient discomfort by avoidance of adenosine, suggesting that iFR may be superior to FFR as a diagnostic tool in clinical practice.

FFR is calculated as the ratio of the distal coronary pressure to the aortic pressure (Pd/Pa) during maximal microcirculatory relaxation, induced by pharmacological vasodilators (hyperemia). The iFR negates the time averaging and administration of vasodilators necessary for FFR by identifying from the resting pressure waveform a period when the native microcirculatory resistance is constant and minimized in diastole. Measurement of Pd/Pa during this time (iFR) is at a point of not only minimal resistance, but also high flow, thus allowing the resistance of an epicardial stenosis to be isolated from the microcirculation.

While iFR has been shown to be non-inferior to FFR, it has a number of inherent limitations. The computational algorithm requires ECG gating or automated landmarking of components of the pressure waveform, thus being limited in clinical scenarios where the ECG is suboptimal or the rhythm is disturbed. Furthermore, iFR assumes that the maximal flow and minimal resistance occurs during diastole, which while true for the left coronary artery, is not constant in the right coronary artery.

Here we aim to determine the accuracy, precision and clinical utility of an adenosine free resting measure of pressure during the point of absolute lowest Pd/Pa during the cardiac cycle, the resting flow reserve (RFR). The RFR represents the maximal relative pressure difference in the cardiac cycle, irrespective of systole or diastole and independent of the ECG, thus negating the limitations of iFR. This measurement thus represents a point of the cardiac cycle when the relative difference between native microcirculatory resistance and the flow is highest, allowing isolation of the resistance across the epicardial stenosis. Moreover, similar to iFR, as the RFR is measured each cardiac cycle it has the ability to display high sensitivity to small pressure changes enabling a pullback at rest separating the contribution of individual stenoses in a coronary vessel with multiple lesions.

By performing the investigations described below, we aim to clarify the validity of RFR, determine its ability to detect ischemia compared to iFR and FFR and place it in

clinical context with specific reference to moderate coronary stenoses of unclear physiological significance.

### Resting Flow Reserve:

The RFR is the point at which the relative difference in the diastolic pressure and the aortic pressure is greatest during the cardiac cycle, thus representing the point at which the native microcirculatory resistance is the lowest and coronary flow is highest (Figure 1).

### Objectives:

3) Compare the agreement of RFR and iFR to detect ischemia in a clinical setting.

[figure not shown]
### Endpoints:

Primary Endpoints:

- The agreement between RFR and iFR for detection of ischemia.

### Secondary Endpoints:

- Lesion classification ( $\leq/ > 0.80$ ) by RFR and iFR
- Pressure drift of RFR and iFR
- Measurement reproducibility for RFR compared to iFR
- Ability to advance to the target lesion and measure RFR and iFR
- 

**Figure 1. Resting Flow Ratio.** A) Pa (red) and Pd (green) wave forms. B) The instantaneous Pd/Pa ratio (blue). C) A filter is applied to the instantaneous Pd/Pa ratio to reduce noise (orange). D) The RFR corresponds to the minimum Pd/Pa during the cardiac cycle (black dash), representing the point at which the native microcirculatory resistance is the lowest and coronary flow is highest.

### Design:

Patients will have both RFR and iFR measured in the following sequence:

- A minimal 6F guiding catheter will be used
- Zero AO transducer and PC
- Flush and zero both wires.

- Deliver 100-200mcg of intracoronary nitroglycerine to maximize epicardial dilation (if clinically indicated)
- Advance the RFR wire to equalize position (guide disengaged)
- Equalize RFR wire
- Advance RFR wire across lesion with the sensor located at least 3 cm distal from the lesion
- Advance the iFR wire to equalize position (guide disengaged)
- Equalize iFR wire
- Advance iFR wire across lesion with the sensor located at least 3 cm distal from the lesion
- Disengage guiding catheter if necessary  
Record basal Pd/Pa
- Record RFR Pd/Pa (RFR value) and iFR Pd/Pa (iFR value)

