**If administration of adenosine is clinically indicated:**

- Administer intravenous adenosine at a rate of 140mcg/min to achieve maximal hyperemia
- Measure hyperemic FFR using RFR and iFR wires
- Stop adenosine
- Wait 3 minutes
- Perform simultaneous resting flow pullback of RFR wire and iFR wire
- Stop recording on both systems

If PCI is indicated perform PCI per standard of care.

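### The measurement sequence names no closing reading for the drift endpoint and no repeat recording for the reproducibility endpoint, and its fixed wire order would alias any between-wire comparison of drift or deliverability

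*Combined protocol and SAP*

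**What the plan says.** The Secondary Endpoints section of the combined protocol and SAP lists, among others, "Pressure drift of RFR and iFR", "Measurement reproducibility for RFR compared to iFR" and "Ability to advance to the target lesion and measure RFR and iFR". Neither drift nor reproducibility is defined. Only the reproducibility item is worded as a comparison.

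The Design section gives one sequence for all patients. Both wires are zeroed. Then comes "Advance the RFR wire to equalize position (guide disengaged", after which the RFR wire is equalized and crosses the lesion. Only then does the plan say "Advance the iFR wire to equalize position (guide disengaged", and the iFR wire is equalized and crosses in turn. With both wires across, the indices are taken in one step: "Record RFR Pd/Pa (RFR value) and iFR Pd/Pa (iFR value".

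The adenosine-conditional block that follows adds hyperemic FFR, a wait, and "Perform simultaneous resting flow pullback of RFR wire and iFR wire". It closes with "Stop recording on both systems".

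The Background says that RFR is obtained on every heartbeat. The Devices section ties each index to one wire system. The Flow Chart's only pressure row refers to FFR and names neither resting index.

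**The concern.** Drift is a change between an opening reference and a later reading at the same place. Reproducibility, in its usual sense, needs the measurement to be made more than once. The sequence supplies the opening reference and one measurement, and names nothing further. A team could follow every written step and finish with no specified reading for drift and no specified repeat for reproducibility. Readings not taken during the procedure cannot be recovered afterwards.

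The secondary matter is order. The RFR wire has always been in place longer since its equalization, and the iFR wire always crosses beside another wire. If drift or deliverability were compared between wires, a difference could reflect the wire or its place in the sequence, and the data could not tell which.

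**Working it through.** **Plan's own figure.** The Power section gives 92 patients for the primary agreement endpoint. It cannot be reproduced without alpha, sidedness, a null agreement and an SD, none of which is stated. This point uses 92 only as the number of patients.

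**1. Endpoints against steps.**
- Drift: one equalization per wire before crossing. No closing reading is specified in Design or in the adenosine block.
- Reproducibility: one fixed-position recording. The only later resting acquisition is the pullback.
- Pullback: it is listed under the adenosine condition, but so is the instruction to stop recording, which must apply to everyone. The layout therefore does not settle whether the pullback is for all patients. Its end point and purpose are not stated.

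**2. Information on repeat variation.** With k recordings in each of n patients, the within-patient SD has n(k − 1) degrees of freedom.
- As written: 92 × (1 − 1) = 0.
- Two recordings in everyone: 92 × (2 − 1) = 92. The 95% limits are √(92/χ²) times the estimate, or 0.87 to 1.17 times, assuming normal errors.

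**3. Comparing the two systems' repeat SDs.** A Pitman-Morgan interval on the repeat differences, for an observed SD ratio of 1 in m patients, extends either way by the factor √(K + √(K² − 1)), where K = 1 + 2(1 − r²)t²/(m − 2), t is the 97.5% point on m − 2 degrees of freedom, and r is the correlation between the systems' repeat differences.

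For m = 92 and r = 0, t = 1.987 and K = 1 + 2 × 3.947/90 = 1.088, so the factor is 1.23. Suppose instead that the pullback served as the repeat, and only in patients given adenosine. Assumed shares of 25%, 50% and 75% give m = 23, 46 and 69.

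| r (assumed) | m = 23 | m = 46 | m = 69 | m = 92 |
|---|---|---|---|---|
| 0 | 1.55 | 1.35 | 1.27 | 1.23 |
| 0.5 | 1.47 | 1.30 | 1.23 | 1.20 |
| 0.8 | 1.31 | 1.20 | 1.16 | 1.13 |

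**4. Order.** Let w be the true wire difference in drift (RFR minus iFR) and d the extra drift of whichever wire goes first. The expected paired difference is w + d with RFR first and w − d with iFR first.
- All 92 RFR first: the mean estimates w + d. In a model with intercept, wire and order, the design matrix has rank 2 of 3.
- 46/46: the average of the two sequence means is [(w + d) + (w − d)]/2 = w, and the rank is 3 of 3.
- Precision, with independent drift of the given SD on each wire: the variance is 2SD²/92 under fixed order, and ¼(2SD²/46 + 2SD²/46) = 2SD²/92 under 46/46. The 95% half-width is 1.96 × √2 × SD/√92 = 0.0029, 0.0058 or 0.0087 for SD 0.01, 0.02 or 0.03.

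The documents give neither d nor the SD, so what follows is a range under assumptions. With w = 0, a two-sided 5% paired t-test under fixed order has noncentrality d/(√2 × SD/√92). The chance of a false wire difference is:

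| d | SD 0.01 | SD 0.02 | SD 0.03 |
|---|---|---|---|
| 0.001 | 10.3% | 6.3% | 5.6% |
| 0.002 | 26.9% | 10.3% | 7.3% |
| 0.005 | 91.9% | 38.9% | 20.1% |

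At a between-wire correlation of 0.5 the nine values run from 6.2% to 99.7%. With a 46/46 list and order in the analysis, simulation (20,000 trials per case) gave 4.6% to 5.1% in all nine.

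**The case against.** The best defence is that usable data may exist. RFR is available beat by beat, so one trace carries some information on variability. The pullback may apply to every patient, and if it ended at the equalize position its last reading could serve as a drift check. Sites may also take a closing reading as routine. The first two possibilities stand, and they rule out the stronger reading that these endpoints cannot be measured at all. They do not close the gap. Beats within one trace do not show agreement between separate measurements. A pullback moves the sensor and has no stated end or role. The documents mention no routine closing reading.

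On order, the defence is stronger. The plan words drift and deliverability so that each wire can be described separately, and it states no between-wire test of either. Five of the nine assumed cases give false-positive rates of only 5.6% to 10.3%, and the 91.9% needs the largest offset with the smallest SD. Even that offset, 0.005, is one tenth of the 0.05 in the Power section, the only difference the plan states. Deliverability bias is not quantified here. Order is therefore a secondary remark.

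Some text may also be missing. The Objectives list begins at item 3 and the Secondary Endpoints list ends in an empty bullet, so a definition could have been lost. The step list in Design reads as complete.

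**Conclusion.** The point holds for drift and reproducibility. Two listed secondary endpoints have no specified reading or repeat behind them, beyond beat-to-beat variation within a single recording. This follows from the sequence itself and needs no assumed number. The size is 0 degrees of freedom for between-recording variation as written, against 92 with one repeat in every patient.

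For order, only a conditional statement is supported: if drift or deliverability is compared between wires, the wire effect is fully aliased with order. The size of any bias cannot be derived from the documents, and the percentages shown rest on assumed drift offsets and SDs.

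Two further inferences are not supported. A reader might conclude that the fixed order biases the primary agreement endpoint, but the RFR and iFR values are recorded in the same step with both wires across the lesion. A reader might also conclude that the pullback is confined to patients given adenosine, but the layout leaves that open. The plan should be corrected for these secondary endpoints; the sample size is not in question here.

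**What to change.** In the Design section:
- **Reproducibility.** In every patient, before any adenosine, take a second, separate resting RFR/iFR recording after a stated interval. The interval matters, because without one the second recording adds little beyond a longer trace. Define reproducibility as the within-patient SD of each index from the two recordings, and compare the systems with a paired method such as Pitman-Morgan on the repeat differences.
- **Drift.** In every patient, record Pd/Pa on both systems just after equalization, and again at the equalize position on withdrawal before recording stops. Define drift as the difference between the two readings, so that no post-equalization value has to be presumed. Flag closing readings delayed because a wire stayed in place for PCI.
- **Order.** Allocate from a 46/46 list which wire is equalized and advanced first. Report drift and deliverability by wire and by order, and include order in any between-wire analysis.

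In the adenosine block, state whether the pullback applies to all patients and whether it ends at the equalize position.

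The cost per patient is a short extra recording, the added equalize-position readings and an entry on an order list. No patients or devices are added. The documents give no procedure times, so the added time cannot be stated exactly.

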**If administration of adenosine is clinically indicated:**

- Administer intravenous adenosine at a rate of 140mcg/min to achieve maximal hyperemia
- Measure hyperemic FFR using RFR and iFR wires
- Stop adenosine
- Wait 3 minutes
- Perform simultaneous resting flow pullback of RFR wire and iFR wire
- Stop recording on both systems

If PCI is indicated perform PCI per standard of care.

**Devices:**

SJM Medical Aeris FFR Pressure wire system for RFR  
Volcano Verrata Pressure wire system for iFR

**Study Population:**

The study population will consist of patients who are referred for coronary angiography and require physiological assessment of intermediate lesions for clinical indications based on the local standard of care. A patient becomes a subject once he/she has been fully informed about the study, has agreed to participate, has signed & dated the consent, and has been determined to meet all the inclusion criteria and none of the exclusion criteria.

1. Inclusion Criteria Age  $\geq$  18 years.
2. Patient provides signed written informed consent before any study-specific procedure.
3. Undergoing coronary angiography, for silent ischemia, stable angina, acute coronary syndrome, or other acceptable indication per the local standard of care.
4. Angiographically 40%-90% stenosis present in at least one native coronary artery.
5. Undergoing physiological assessment for standard clinical or diagnostic indications

## Exclusion Criteria

1. Aorto-ostial lesion location within 3 mm of the aorta junction (both right and left).
2. Left main stenosis
3. Vessel(s) and lesion(s) not amenable for PCI, for example diffuse disease.
4. Saphenous vein graft, chronic total occlusion
5. Haemodynamic instability at the time of intervention (heart rate<50 beats per minute, systolic blood pressure <90mmHg), balloon pump
6. Currently participating in another clinical study that interferes with study results.
7. Pregnant or nursing subjects and those who plan pregnancy in the period up to 1 year following index procedure.
8. Any other medical condition that in the opinion of the investigator will interfere with patient safety or study results.
9. High degree A-V block, sinus node disease.
10. Asthma/COPD with active wheeze
11. Known hypersensitivity to adenosine
12. STEMI within 48 hours.

## **Power:**

The primary hypothesis is:

Null-

- mean RFR measurements = mean iFR measurements
- $\Delta \pm 0.05$

A sample size of 92 patients will provide 90% power to detect a 95% agreement between RFR and iFR to detect ischemia

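### The stated primary null (equal mean RFR and iFR) does not test the primary endpoint, agreement on ischemia, and the power claim belongs to a different hypothesis

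*Combined protocol and SAP*

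**What the plan says.** The combined protocol and SAP describes the primary question in four places.

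- Objectives: "Compare the agreement of RFR and iFR to detect ischemia in a clinical setting".
- Endpoints, primary: "The agreement between RFR and iFR for detection of ischemia". The visible text attaches no agreement statistic and no ischemia cut-off to it.
- Power, null hypothesis: "mean RFR measurements = mean iFR measurements". A delta of plus or minus 0.05 stands on the next line, without a label.
- Power, sample size: "A sample size of 92 patients will provide 90% power to detect a 95% agreement between RFR and iFR to detect ischemia".

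The only cut-off in the visible text belongs to a secondary endpoint: "Lesion classification ( $\leq/ > 0.80$ ) by RFR and iFR". The visible text gives no alpha, sidedness, SD of the paired difference, reference agreement rate or success rule.

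**The concern.** The null concerns two averages. The objective, the endpoint and the power sentence concern whether the same lesion gets the same ischemia call from both indices. Opposite errors cancel in a mean, but each one can be a discordant call, so close means do not establish agreement.

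The Power section therefore holds three elements (the null, the 0.05 and the 95%) that the visible text does not tie to one test. An analyst who tests the null, one who uses 0.05 as an equivalence margin, and one who estimates the proportion classified alike could reach different primary conclusions from the same data. If that choice is made after the data are seen, the primary result is not confirmatory.

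**Working it through.** **Inputs from the plan:** 92 patients, both indices in each patient (Design), 95% agreement, 90% power, 0.05. **Assumed, because the plan gives none:** alpha, reference agreement rate, paired SD, bias and the distribution of the indices.

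**1. The plan's own figure, read as a test of a proportion.** Let X be the number of 92 patients classified alike, with true agreement 0.95. The exact (Clopper-Pearson) lower bound is the 0.025 quantile of Beta(x, 92 - x + 1), or the 0.05 quantile for a one-sided 0.05 test. Success requires that bound to exceed the reference; power is P(X >= x).

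| Smallest x for success | Lower bound, two-sided 95% CI | Power at 0.95 | Example reference cleared |
|---|---|---|---|
| 85 | 0.8495 | 91.0% | 0.84 |
| 86 | 0.8634 | 82.3% | 0.85 |
| 87 | 0.8777 | 68.8% | 0.87 |
| 88 | 0.8924 | 51.0% | 0.88 |
| 89 | 0.9077 | 31.9% | 0.90 |

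At one-sided 0.05, x = 85 clears 0.86 (91.0%), and 0.90 needs x = 88 (51.0%). So 92 patients and 90% power fit a reference up to about 0.849 (two-sided 95% CI) or about 0.86 (one-sided 0.05). If the 0.05 was meant on the agreement scale, 0.95 against 0.90, power is 32% or 51%.

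**2. The null as written, with the 0.05 line set aside.** Paired t test, two-sided 0.05, noncentrality = offset / SD x sqrt(92). For an offset of 0.01 and SD 0.03 this is 0.01 / 0.03 x 9.592 = 3.20, and equality is rejected 89% of the time. At SD 0.02 and 0.05 the figures are 99.7% and 48%. An offset one fifth the size of 0.05 would thus often count as a difference, and noisier data would make equality harder to reject.

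Some offset is to be expected from the plan's definitions. For one index, "The RFR corresponds to the minimum Pd/Pa during the cardiac cycle"; the other is taken in "a period when the native microcirculatory resistance is constant and minimized in diastole". Apart from filtering and the two wire systems, RFR should tend to lie at or below iFR. The plan does not give the size of that offset.

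**3. The 0.05 as an equivalence margin on the mean difference.** Two one-sided tests, each at 0.05, pass if mean difference +/- 1.662 x SD / sqrt(92) lies within +/-0.05. At bias -0.03 and SD 0.03, the expected lower limit is -0.03 - 1.662 x 0.03 / 9.592 = -0.035, so the test passes almost always.

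The proportion classified alike was simulated with iFR normal, truncated at 1 (assumed mean 0.86-0.90, SD 0.07-0.10), RFR = iFR + N(bias, 0.03) capped at 1, and 0.80 used for both indices for illustration only.

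| Bias | SD | Equivalence test passes | Classified alike |
|---|---|---|---|
| 0 | 0.03 | about 100% | 90-94% |
| -0.02 | 0.03 | about 100% | 86-91% |
| -0.03 | 0.03 | about 100% | 83-88% |

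Passing this test is compatible with agreement clearly below 95%.

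**4. The 0.05 as a bound for limits of agreement.** Limits are mean +/- 1.96 SD, each with standard error SD x sqrt(1/92 + 1.96^2 / (2 x 91)). Requiring the 95% CIs of both limits to lie inside +/-0.05 gives power of about 91% at bias 0 and SD 0.019, 49% at bias 0 and SD 0.021, and 16% at bias -0.01 and SD 0.019. This reading can also give about 90%, but only for a particular SD that the plan does not state.

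**The case against.** The strongest reply is that the 0.05 sits directly under the null, so the natural reading is a loosely worded equivalence hypothesis and bare equality was never meant. That is fair, and the rejection rates in step 2 apply only if that line is ignored. It does not rescue the text: in an equivalence test equal means is the alternative, and the test still addresses average bias. A reader might infer that the trial would report a non-significant difference as agreement; no section says so.

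A reader might also infer that 90% power at 92 patients is an error. The documents do not support this. Step 1 reproduces it for references that the plan could have intended but does not state. The failure against 0.90 counts only if 0.90 was meant.

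Third, the 0.80 classification is listed separately as secondary, which suggests that the primary may mean numerical agreement. This stands in part, and the visible text does not make binary concordance the only acceptable primary. But the objective, the endpoint and the power sentence all refer to detecting ischemia, and a test of means does not measure numerical agreement either.

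Fourth, the biases, SDs and distributions are assumed, and filtering or the two wire systems could offset the expected direction of bias. The zero-bias row is shown for that reason. Finally, the visible objectives begin at item 3 and one secondary bullet is empty, so every statement here about missing inputs is limited to the visible text. The null itself is legible.

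**Conclusion.** The concern holds in this form: the stated primary null does not test the primary endpoint, and the 90% power belongs to a different hypothesis from that null. This must be fixed, because it is the only primary hypothesis in the visible text and the conclusion depends on which reading is followed.

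The mismatch rests on the wording alone. Its practical size rests on assumptions: under those in step 3, an equivalence test of means passes almost always with 83-88% classified alike at bias -0.03, and with 90-94% even at zero bias. The power figures in step 1 are exact for independent patients with true agreement of 95%. They show the sample size claim to be incompletely specified, not wrong.

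**What to change.** In the Power section, replace the equality null with one hypothesis that matches the primary endpoint.

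- **Form that fits the plan's own power sentence:** the proportion of patients given the same ischemia classification by both indices, with an exact two-sided 95% CI, and success if the lower bound exceeds a minimum that the sponsor states in advance and justifies. Use one pre-specified lesion per patient, because eligibility allows several: "Angiographically 40%-90% stenosis present in at least one native coronary artery".
- **Cut-offs:** state the one used for each index, and say how this analysis differs from the secondary classification endpoint.
- **If numerical agreement was meant:** make Bland-Altman limits of agreement against +/-0.05 the primary analysis, with the SD assumed for its power, in place of a test of means.
- **The 0.05:** label it. An equivalence test of the mean difference can stay as a supporting analysis only.
- **Power:** restate it with alpha, sidedness and reference value. The table in step 1 gives examples for 92 patients, not recommended minimums.

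No new measurements are needed, since the Design section already records both values. The cost is that the sponsor must justify a minimum agreement, and the stated power falls if it is above about 0.85. Keeping 90% power at true agreement of 95% with the two-sided 95% CI would then take about 93-102 patients for 0.85, 171-181 for 0.88 and 292-316 for 0.90. Each range runs from the first size reaching 90% to the size from which power stays there.
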